## 1 Introduction

This document describes the content proposed for the primary statistical analysis of ACTG A5327. The focus of this analysis will address the primary safety and efficacy objectives for Cohort 2 (8 weeks of treatment) as well as the secondary objectives for which data will be available at the time of the primary analysis. Details about analyses for review by the Study Monitoring Committee (SMC) are not included in this SAP as all participants had completed study treatment by the time of preparation of this SAP and no further reviews of the study by the SMC were to be undertaken.

## 2 Study Overview

### 2.1 Study Schema

#### (Extracted from Protocol Version 2.0)

#### DESIGN

SWIFT-C is a Phase I, open-label, two-cohort clinical trial, in which between 44 and 50 acutely HCV-infected HIV-1 positive participants will be enrolled and administered oral sofosbuvir (SOF) in combination with weight-based ribavirin (RBV, cohort 1) or ledipasvir (LDV, cohort 2).

The study will investigate the safety and efficacy of two SOF-containing regimens and will assess if the addition of a second DAA allows for a shortened course of therapy. The study will open the first cohort with sofosbuvir plus ribavirin (SOF+RBV) for 12 weeks and with a planned accrual of at least 17 participants. The second cohort will open with ledipasvir/sofosbuvir (LDV/SOF) for an 8-week treatment. The second cohort will include at least 27 participants. Each cohort will occur in two steps: on treatment (Step 1) and followup (Step 2). The cohorts will enroll sequentially.

#### DURATION

32-36 weeks (8-12 weeks on-treatment followed by 24 weeks of follow-up)

#### SAMPLE SIZE

A minimum of 44 participants will be enrolled in Cohort 1 and Cohort 2.

Cohort 1: Minimum of 17 participants will be enrolled.

Cohort 2: Minimum of 27 participants will be enrolled.

If a participant is discontinued from study treatment for non-virologic reasons or is not evaluable for SVR12 while enrollment is ongoing to the same cohort, then an additional participant may be enrolled to that cohort to help ensure that an adequate number complete study treatment and are evaluable for SVR12, up to a maximum enrollment of 50 participants.

#### POPULATION

HIV-1 coinfecting individuals who have acute HCV infection or reinfection and have any genotype (Cohort 1) and genotype 1 or 4 (Cohort 2).

#### REGIMEN

Cohort 1: SOF 400mg once daily and weight-based RBV (1000 or 1200 mg daily in two divided doses).

Cohort 2: Daily fixed combination pill of LDV/SOF (90mg/400mg).

## 2.2 Hypothesis

An interferon sparing regimen of sofosbuvir (SOF) and ribavirin (RBV) and/or ledipasvir/sofosbuvir (LDV/SOF) can achieve sustained virologic response (SVR) 12 rates that are noninferior to the current standard of care assessed by historical control for the treatment of acute HCV in HIV-1/HCV co-infected individuals with an improved safety profile and a shorter length of treatment.

## 2.3 Primary Objectives

1. To evaluate HCV treatment response to SOF and weight-based RBV (1000 or 1200 mg daily in two divided doses) taken for 12 weeks and daily LDV/SOF taken for 8 weeks as assessed by SVR12, defined as HCV RNA undetectable [ $<$ lower limit of quantification (LLOQ) target not detected (TND)] 12 weeks post-treatment in persons with existing HIV-1 infection who are acutely infected with any HCV genotype (Cohort 1) or Genotype 1 or 4 (Cohort 2).
2. To evaluate the safety and tolerability of combination oral antiviral therapy with SOF and weight-based RBV taken for 12 weeks and daily LDV/SOF taken for 8 weeks in persons with existing HIV-1 infection who are acutely infected with any HCV genotype (Cohort 1) or Genotype 1 or 4 (Cohort 2).

## 2.4 Secondary Objectives

1. To evaluate the antiviral efficacy of SOF and weight-based RBV and LDV/SOF as measured by the proportion of participants with HCV RNA undetectable ( $<$ LLOQ TND) at weeks 1, 2, 4, 8, 12 and at 2 (SVR2), 4 (SVR4), 8 (SVR8), 12 (SVR12) and 24 (SVR24) weeks post-treatment.
2. To evaluate evidence of relapse, defined as HCV RNA undetectable ( $<$ LLOQ TND) at end-of-treatment but HCV RNA quantifiable ( $\geq$ LLOQ) during followup.
3. To assess the emergence of viral resistance to SOF and LDV when administered with RBV for acute HCV infection.
4. To estimate RBV pharmacokinetics (PK) and evaluate covariates (including concomitant antiretroviral drugs) which may affect RBV PK. (Cohort 1 only)
5. To assess the relationship of viral clearance and RBV PK (Cohort 1) with baseline predictors including genetic polymorphisms (eg., IL28B and ITPA), expression of key host immune response genes and proteins.

6. To assess the effects of LDV on PK or tenofovir (TFV) in persons on tenofovir disoproxil fumarate (TDF)-containing regimens. (Cohort 2 only)
7. To evaluate participants' adherence by using several tools, including self-report, pill count, and drug concentrations.
8. To evaluate the hypothesis that successful direct-acting antiviral (DAA)-based therapy alleviates type I (IFN)-induced immune dysfunction during acute HCV infection.

## 2.5 Visit and Evaluation Schedule

The Cohort 2 expected schedule for on-treatment clinic visits is shown in Table 1 and the expected schedule for post-treatment follow up clinic visits is shown in Table 2 below. Unless otherwise noted, analyses by A5327 study week will utilize these study week definitions (defined in days); the start time for calculation of study week will be the date of first dose of treatment.

**Table 1: Weeks Since Starting Treatment**

	Baseline	Week 1	Week 2	Week 4	Week 8
Days	0	4-10	11-17	21-42	49-70

**Table 2: Weeks Since Starting Post-Treatment Follow up**

	Week 0	Week 2	Week 4	Week 8	Week 12	Week 24
Days	Last day of treatment	9-22	23-49	51-78	79-112	161 onwards

## 2.6 A5327 Protocol History

**The analysis described in this SAP concerns only Cohort as defined in protocol version 2.0:**

### **Cohort 2:**

Protocol Version 2.0 (finalized on July 2, 2015)

A5327 Clarification Memo 1, Version 2.0 (10/08/15) regarding negative pregnancy tests.

## 2.7 General Statistical Considerations

Key analysis decisions:

- Throughout, study entry is defined at the date of entry visit as recorded as the header date on the ADM0010.

- The analyzed measurement will, in general, be the measurement closest to the scheduled evaluation time, and the acceptable windows will be based on time since first study treatment dose.
- Data summaries and analyses will be presented for Cohort 2 only (the analysis of data for participants in Cohort 1 are included in a separate report).

Notes for conventions used in the primary analysis report:

- For the primary analysis report:
  - Lists will be sorted by variables in the order given with study participants identified using an alternate patient identifier (PubID, i.e. not ACTG patid).
  - Participant-specific dates will not be shown, but converted to time since start of study treatment (all participants did start study treatment).
- Each Table/Figure/Listing will be annotated with the name and location of the program used to create it.
- Validation:
  - Tables/figures requiring SDAC validation of the program used to generate the results will be flagged with “[V]”.
  - Tables/figures requiring independent programming of results by the SDAC validator will be flagged with “[IP]”.

### **3 Accrual and Screening [V]**

Purpose : To give a summary of accrual and the distribution of enrollment across sites.

- a) Table: Number (%) enrolled overall and by month

Note: Dates of first and last enrollments will be provided in a footnote to the table

- b) Table: Number (%) enrolled by enrolling site  
c) List: participants who were screened by did not enter the study (screen failures)

### **4 Eligibility Violations and Exclusions [V]**

Purpose: To document why any participants who were enrolled were subsequently excluded from analysis and document any other exclusions.

- a) List: violations of eligibility criteria by site and details of exclusions from analyses (if any)  
b) List: participants who did not have treatment dispensed. These participants will be excluded from the analysis.

### **5 Baseline Characteristics [V]**

Purpose: To describe the study population

Baseline characteristics will be analyzed as continuous or as categories or both, as appropriate. Tables will provide # of participants, # of missing data points, median, quartiles (Q1-Q3), minimum, maximum for the continuous variables (with transformations as appropriate) and number (%) for the categorical variables. In calculation of percentages, participants with missing data will not be included in the denominator.

a) Table summarizing demographic characteristics

- i. Sex (STATUS): number (%)
- ii. Self-reported race/ethnicity (STATUS): number (%)
- iii. Age on the day of study entry (years) (STATUS): N, median, 1st and 3rd quartile, minimum and maximum; number (%) by age group (18-19, 20-29, 30-39, 40-49, 50-59; 60-69; 70+ years, rounded down)
- iv. Intravenous drug use (IVD) history (STATUS): number (%) by group (Never, current, previous user)
- v. Weight (kg) (F0033): N, median, 1st and 3rd quartile, minimum and maximum
- vi. BMI (kg/m^2): number (%) by BMI group (Underweight[<18.5], normal [18.5-24.9], overweight [25-29.9], obese [>30])

b) Table summarizing HCV disease status

- i. Infection status (ANSTAB): number (%) by new acute HCV infection and HCV reinfection
- ii. Acute HCV eligibility (ANSTAB): number (%) meeting one of the acute HCV infection criteria from protocol section 4.1.2
- iii. Time from first laboratory evidence of acute HCV to entry (days) (ANSTAB): N, median, 1st and 3rd quartile, minimum and maximum
- iv. Time from diagnosis of acute HCV to entry (days) (DF0002): N, median, 1st and 3rd quartile, minimum and maximum
- v. Baseline HCV RNA (IU/ml) and corresponding results for log10 copies/ml (F3116): N, median, 1st and 3rd quartile, minimum and maximum  
Note: Baseline is defined as the value at A5327 entry
- vi. Baseline HCV RNA: number (%) undetectable and detectable, number (%) < 6 million IU/mL and ≥6 million IU/mL  
Note: undetectable at baseline may indicate spontaneous clearing occurring between screening and baseline.
- vii. HCV genotype (SRW0028): number (%) by category (1a, 1b, 2a, 2b, 3, 4, 5, 6)
- viii. IL28B genotype (GENOHUM): number (%) by category (CC, CT, TT)  
Note: Batch tested at the end of study.

c) Table summarizing HIV disease status

- i. Baseline HIV-1 RNA (copies/ml) (RNALDMS): number (%) by category (<50 copies, ≥50 copies)  
Note: Baseline is defined as the closest value on/before date of start of study treatment.

- ii. Baseline CD4+ cell count (/mm^3) (LBW0054): N, median, 1st and 3rd quartile, minimum and maximum;  
Note: Baseline is defined as the arithmetic mean of screening and entry values or, in the absence of one value, the one available.
  - iii. Baseline CD4+ cell percent (LBW0054): N, median, 1st and 3rd quartile, minimum and maximum;  
Note: Baseline is defined as the arithmetic mean of screening and entry values or, in the absence of one value, the one available.
- d) Table summarizing HIV-1 antiretroviral therapy (ARVs)
- i. Receiving HIV ARVs prior to entry (ANSTAB): number (%) yes and no
  - ii. HIV ARV regimen at entry (TXT0004): number (%) on each regimen
  - iii. HIV ARV regimen of interest for renal functions (TXT0004): number (%) on TDF + boosted PI, COBI, and other ARV regimens
  - iv. NNRTIs (TXT0004): number (%) on efavirenz, rilpivirine, tenfovir, and abacavir based regimens
  - v. Integrase Inhibitors (IIs) (TXT0004): number (%) on raltegravir and dolutegravir based regimens
  - vi. Protease Inhibitors (PIs) (TXT0004): number (%) on boosted PI based regimens
- e) Table summarizing baseline laboratory evaluations
- For each laboratory evaluation the following will be presented unless otherwise specified: N, median, 1st and 3rd quartile, minimum and maximum. If the lab value is graded, DAIDS grading scale will also be presented.
- Note: Baseline is defined as the last available value on or before the date of starting study treatment. Fasting per protocol is defined as nothing to eat or drink except prescription medications and water for at least 8 hours prior to the procedure. If nonfasting at the screening visit, the participant should return within 7 days for fasting blood draw. These panels are performed at the designated testing laboratory; see A5237 lab processing chart [LPC] for directions.
- i. Hematology characteristics (F2850): hematocrit, hemoglobin (g/dL), platelets (cells/mm^3), red blood cell (RBC) count, white blood cell (RBC) count (cells/mm^3), WBC differentials (absolute and percentage: lymphocytes, monocytes, neutrophils, eosinophils, basophils, reticulocyte count) and mean corpuscular volume (MCV).
  - ii. Chemistry characteristics(F2841): alanine aminotransferase (ALT/SGPT), aspartate aminotransferase (AST/SGOT), albumin (g/dL), alkaline phosphatase, creatinine, total bilirubin, direct bilirubin, glucose (mg/dL), lipase, potassium (mEq/L), thyroid-stimulating hormone, sodium(mEq/L) and gamma-glutamyl transferase.
  - iii. Calculated creatinine clearance(LBW0060)
  - iv. Fasting Lipids (LDMS table TBD): low density lipoprotein (LDL, mg/dL), high density lipoprotein (HDL, mg/dL), triglycerides (TG, mg/dL), total cholesterol (TC, mg/dL), and apolipoproteins B, E, and CII.

- v. Coagulation Markers (F2850): INR, prothrombin time (PT), activated partial thromboplastin (APTT)
  - vi. Urinalysis (F0869): appearance, blood, color, glucose, leukocyte esterase, PH, protein, urobilinogen
- f) Table summarizing history of sexually transmitted infections (STIs)
- i. Reported History of STI Diagnosis (DF0002): number (%) with history of STIs and no history of STIs. Within history of STIs, number (%) for each type of STI. Refer to A5327 Targeted Diagnosis list on the protocol specific web page, under Genitourinary/Sexually Transmitted Diseases, with the addition of acute Hepatitis B, herpes simplex virus and cervicitis.

## 6 Study status and loss to follow up [V]

Purpose: To summarize extent of follow-up on study.

- a) CONSORT diagram: number of participants enrolled, number who started treatment, completed treatment, and completed study
- b) Table: On study treatment number (%) by category (F4003 and F1601)  
Categories included are:
  - i. Completed planned treatment period and post treatment follow-up
  - ii. Completed planned treatment period but off study early
  - iii. Discontinued study treatment early and completed planned post treatment follow-up
  - iv. Discontinued study treatment early and discontinued post treatment follow-up early
- c) List: Reasons off study treatment early (include both the category and text field from F4003)
- d) List: Reasons off study early (include both the category and text field from F1601)

## 7 Study conduct [V]

Purpose: To summarize how compliant participants are with study visits  
Table: summarize missed visits reflected as the number (%) of expected and observed clinic visits

## 8 Primary Endpoint Analyses

### 8.1 Efficacy Outcome [IP]

Note: For clarity of presentation, results for the primary efficacy outcome and for the secondary efficacy outcomes concerning HCV RNA will be presented together in the analysis report.

Primary Outcome Measure (from protocol section 9.2.1.1)

SVR12 is defined as HCV RNA undetectable (<LLOQ TND) of the assay at 12 weeks after date of last dose of study treatment.

The 12 week measurement will be the measurement obtained closest to 84 days (i.e. 12\*7 days), within the window 79 to 112 days inclusive after study treatment discontinuation. This analysis will be intent to treat (ITT) analysis.

If a participant has no HCV RNA measurement within this window, then the participant will be considered as having detectable HCV RNA at 12 weeks unless the preceding and subsequent HCV RNA measurements are both undetectable (<LLOQ TND).

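### Does scoring SVR12 without regard to HCV RNA at entry credit treatment with clearance that came before the first dose?

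*SAP*

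**What the plan says.** Section 8.1 of the SAP defines the primary efficacy outcome: "SVR12 is defined as HCV RNA undetectable (<LLOQ TND) of the assay at 12 weeks after date of last dose of study treatment". The analysis is intent to treat. If there is no result in the 79 to 112 day window, "the participant will be considered as having detectable HCV RNA at 12 weeks unless the preceding and subsequent HCV RNA measurements are both undetectable". A second table, the Completer analysis, is restricted to participants evaluable for SVR12 and leaves out those who stopped treatment early for nonvirologic reasons. Section 9.1 scores weeks 1, 2, 4 and 8, and Section 9.2 scores the other post-treatment times, also by undetectability at the time concerned. None of these definitions refers to the entry value.

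Section 5 b) vi plans this tabulation: "Baseline HCV RNA: number (%) undetectable and detectable". Its note adds that "undetectable at baseline may indicate spontaneous clearing occurring between screening and baseline".

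Section 4 states one exclusion rule: "participants who did not have treatment dispensed. These participants will be excluded from the analysis". It also provides for listing any other exclusions, but ties none to HCV RNA at entry. The hypothesis in Section 2.2 is that SVR12 is "noninferior to the current standard of care assessed by historical control".

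**The concern.** Read together, Sections 5 and 8.1 seem to leave a gap. The SAP foresees that someone may have cleared the virus between screening and entry. It then counts that person as a responder if they are still undetectable 12 weeks after the last dose. Cohort 2 has no concurrent control and its result is to be read against a historical rate, so clearance before dosing would be reported together with response to treatment. Week 1 would be more exposed than SVR12, because a participant already undetectable at entry counts as an early antiviral response when few others may have reached that point. The Completer analysis, as worded here, does not separate these participants. At stake would be an SVR12 proportion, and early on-treatment proportions, that overstate what the regimen did.

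**Working it through.** **Does any passage contradict another?** The definition in Section 8.1 matches objective 1 in Section 2.3: both turn on undetectability 12 weeks after treatment. The note in Section 5 explains a baseline category. It promises no separate efficacy analysis, so Sections 8.1 and 9.1 break no commitment. Under intent to treat, a participant who was enrolled and treated stays in the denominator. Removing people on an entry value would be a departure that needs its own justification, particularly since one undetectable result does not prove clearance.

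**What would the reader of the report see?** Section 5 gives the number and percentage undetectable at entry. Section 9.1 adds a trajectory for each participant and an appendix with every HCV RNA value by week. With a cohort of about 27, a reader can identify any such participant and recalculate the proportion.

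**How large could the effect be?** The SAP gives no expected SVR12, historical rate or margin, so there is no figure of its own to reproduce. Inputs:

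- N = 27, the stated minimum for Cohort 2 (Section 2.1, Sample Size).
- k = number undetectable at entry. Assumed 1 to 3; the SAP gives no count.
- p = SVR12 rate in participants detectable at entry. Assumed 0.75 to 0.95.
- Interval: two-sided 90% Blyth-Still-Casella (Section 8.1).

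If all k are scored as successes, the intent-to-treat proportion is [k + p(27 − k)]/27. Subtracting p leaves a shift of k(1 − p)/27.

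| k | p = 0.95 | p = 0.90 | p = 0.75 |
|---|---|---|---|
| 1 | 0.05/27 = 0.2 points | 0.10/27 = 0.4 | 0.25/27 = 0.9 |
| 2 | 0.10/27 = 0.4 | 0.20/27 = 0.7 | 0.50/27 = 1.9 |
| 3 | 0.15/27 = 0.6 | 0.30/27 = 1.1 | 0.75/27 = 2.8 |

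The shift is zero if k = 0 or p = 1.

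Whole-number cases:

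- k = 1: 25/27 = 92.6% against 24/26 = 92.3%, a difference of 0.3 points. Lower 90% limits are 0.796 and 0.791.
- k = 3: 25/27 = 92.6% against 22/24 = 91.7%, a difference of 0.9 points. Lower limits are 0.796 and 0.779.
- All respond, k = 3: 27/27 and 24/24 are both 100%. Lower limits are 0.899 and 0.885, and they differ only because the subset is smaller.
- Opposite direction, k = 1 scored a failure under the missing-data rule: 24/27 = 88.9% against 24/26 = 92.3%, a difference of −3.4 points. This reflects the handling of a missing result and has nothing to do with clearance.

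For comparison, the interval at 25/27 runs from 0.796 to 0.980, a width of 0.184 or about 18 points.

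**On-treatment weeks.** Let q be the assumed proportion of participants detectable at entry who are undetectable at the week concerned. The shift is k(1 − q)/27. For k = 1 it is 0.90/27 = 3.3 points at q = 0.10 and 0.50/27 = 1.9 points at q = 0.50. For k = 3 it is 2.70/27 = 10.0 and 1.50/27 = 5.6 points.

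**The case for a change.** The best argument for raising the point is that the SAP itself names the circumstance and then plans no estimate that allows for it. A restricted proportion with its interval would cost one row in Section 8.1 and one column in Section 9.1, from data already being assembled. Stated in advance, it would be more credible than a subset chosen after the results are known. The on-treatment proportions are meant to show antiviral efficacy, and there the assumed shift reaches 10 points.

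Part of this stands. No such estimate is listed, and early on-treatment proportions could move by several points if such participants exist. Four things keep it from being a fault:

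- The larger shifts need assumed values of both k and q, and they fall on secondary descriptive proportions to which the SAP attaches no threshold.
- The subset would not isolate the treatment effect. Clearance after entry would remain in it, and a participant who had not truly cleared could be removed. The SAP does not say whether the historical series left out such patients, so restricting one side need not improve the comparison.
- The gain from stating it in advance is limited. Section 1 says that all participants had completed treatment when the SAP was prepared, so in this open-label study the entry samples had already been taken.
- Evaluability for SVR12 governs the Completer analysis and also appears in the Sample Size text, where an additional participant may be enrolled if one "is not evaluable for SVR12 while enrollment is ongoing to the same cohort". This document does not define the term. The protocol, which is not at hand, may do so, and it holds the eligibility criteria. Whether the Completer set already deals with these participants therefore cannot be settled from the SAP.

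**Conclusion.** The concern does not hold. Section 8.1 states an intent-to-treat endpoint consistent with its objective, and Section 5 discloses the one baseline feature that could affect how it is read. Followed as written, the plan gives a sound SVR12 estimate together with the information needed to interpret it. Under the assumptions k = 1 to 3, N = 27 and all k scored as successes, SVR12 moves by 0.2 to 1.1 points at p = 0.90 to 0.95 and by 0.9 to 2.8 points at p = 0.75, against an interval about 18 points wide at 25/27. The movement is zero if nobody is undetectable at entry, and the SAP does not say that anybody is. Because it gives no historical rate or margin, no changed conclusion can be shown. A supplementary estimate in participants detectable at entry is a reasonable option for the report, but its absence is not a defect.

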### 9.2 HCV RNA during follow-up [V]

Secondary Outcome Measure (from protocol section 9.2.2.2)

HCV RNA undetectable (<LLOQ TND) at 2 (SVR2), 4 (SVR4), 8 (SVR8), and 24 (SVR24) weeks after last dose of study treatment. The windows for these measurements will be 9 to 22, 23 to 50, 51 to 78, and 161 days onwards. If there is more than one measurement within a window, then the measurement closest to the targeted time will be used. If there is no measurement within a window, then the participant will be considered as having detectable HCV RNA at the targeted time, unless (for weeks 4 and 8) the preceding and subsequent HCV RNA measurements are both <LLOQ TND.

Planned Analysis

Note: For clarity of presentation, results for the primary outcome measure (SVR12) will be included in the following tables.

- a) Table: summarize the proportion of HCV undetectable (<LLOQ TND) of the assay at 2 (SVR2), 4 (SVR4), 8 (SVR8), 12 (SVR12) and 24 (SVR24) weeks after last dose of study treatment. A 90% two-sided confidence interval will be provided around the observed proportions (HCVRNALDMS)
- b) Figure: summarize the proportion of HCV undetectable, with the upper and lower limit of the confidence interval at 2 (SVR2), 4 (SVR4), 8 (SVR8), 12 (SVR12) and 24 (SVR24) weeks after last dose of study treatment (HCVRNALDMS).

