### 9.3 HCV RNA Relapse [V]

#### Secondary Outcome Measure (from protocol section 9.2.2.3)

To evaluate virologic evidence of relapse, defined as HCV RNA undetectable (<LLOQ TND) at end-of-treatment but HCV RNA quantifiable ( $\geq$ LLOQ) during followup, will require confirmation and should be performed as soon as possible but within 2 weeks after determination of initial observation.

For analysis purposes, confirmatory values obtained after 2 weeks will be included.

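### The SVR scoring rule has no exception for a confirmed relapser who has started non-study HCV therapy; SVR24 is the main exposure, SVR12 only narrowly

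*SAP*

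**What the plan says.** Section 8.1 defines SVR12 as "HCV RNA undetectable (<LLOQ TND) of the assay at 12 weeks after date of last dose of study treatment". One sample decides it: "The 12 week measurement will be the measurement obtained closest to 84 days", taken "within the window 79 to 112 days inclusive after study treatment discontinuation". Failure without a detectable sample is assigned in one situation only: "If a participant has no HCV RNA measurement within this window, then the participant will be considered as having detectable HCV RNA at 12 weeks". Even that is waived when the samples on either side are both undetectable.

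Section 9.2 applies the same logic to the other follow-up time points: "The windows for these measurements will be 9 to 22, 23 to 50, 51 to 78, and 161 days onwards", and "If there is more than one measurement within a window, then the measurement closest to the targeted time will be used". Its bracketing waiver covers weeks 4 and 8 only, so a missing week 24 sample is a failure.

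Section 9.3 treats relapse as an outcome of its own, "defined as HCV RNA undetectable (<LLOQ TND) at end-of-treatment but HCV RNA quantifiable" in follow-up, subject to confirmation. The only planned output is a listing.

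The SAP does not mention non-study HCV therapy. The Completer Analysis in section 8.1 drops only those who stopped study treatment early for nonvirologic reasons, so it does not deal with this case.

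**The concern.** Sections 8.1 and 9.2 together give a complete algorithm that a programmer can follow without further instruction. It looks at each time point in isolation. A participant whose relapse is confirmed, who then starts another HCV regimen and becomes undetectable on or after it, passes the test at the next time point. The same person appears in the section 9.3 listing as a relapse and in the section 8.1 or 9.2 tables as a success.

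The first primary objective (section 2.3) is to evaluate response to LDV/SOF taken for 8 weeks. Undetectable RNA obtained with a different regimen after relapse is not that response. The plan is also uneven: an unbracketed missing sample is a failure, yet a documented and re-treated relapse can be a success. The misclassification can only raise the reported rate, and the cohort is small and has no concurrent control. The SAP was written after all participants had completed study treatment (section 1), so a rule left open now would be settled when outcomes may already be known.

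**Working it through.** The SAP gives no figure to reproduce here, so the check is to apply the rule as written and then size one misclassified participant.

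**Inputs.** SVR12 window days 79–112, target day 84 (8.1). SVR24 window from day 161, no upper limit (9.2), target 24 × 7 = day 168. Confirmation of relapse due within 2 weeks (9.3). Cohort 2 minimum 27; total maximum 50; Cohort 1 minimum 17 (2.1). Two-sided 90% interval by Blyth-Still-Casella for SVR12 (8.1).

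**Step 1: the rule applied to hypothetical RNA courses** (days after last dose)

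| Course | SVR12 | SVR24 |
|---|---|---|
| Quantifiable day 28, confirmed day 35, re-treated, undetectable days 84 and 168 | yes | yes |
| Undetectable to day 56, quantifiable day 84, re-treated, undetectable day 200 | no | yes |
| Quantifiable day 28, confirmed, re-treated, undetectable day 70, no sample days 79–112, undetectable day 168 | yes, by bracketing | yes |
| Quantifiable day 28 and still quantifiable at days 84 and 168 | no | no |

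In the second course, a sample at day 168 instead of day 200 gives the same result, because both lie in the SVR24 window. The last course shows that a relapser who is still viraemic is scored correctly.

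**Step 2: is the timing possible?** Allow the full 14 days for confirmation.

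| First quantifiable result | Confirmed by | Days left to day 84 | Days left to day 168 |
|---|---|---|---|
| Day 28 (week 4) | 28 + 14 = 42 | 84 − 42 = 42 | 168 − 42 = 126 |
| Day 56 (week 8) | 56 + 14 = 70 | 84 − 70 = 14 | 168 − 70 = 98 |
| Day 84 (week 12) | 84 + 14 = 98 | already a failure | 168 − 98 = 70 |

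As an assumption, take a second course of the lengths used in this study, started on day 42. An 8-week course ends at 42 + 56 = day 98 and a 12-week course at 42 + 84 = day 126, both before day 161. The course need not be finished, since an undetectable result on therapy also satisfies the rule. SVR24 is therefore reachable after relapse at any of these three visits. SVR12 needs an early relapse, prompt therapy and quick suppression.

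**Step 3: size of one case.** At minimum enrolment, 1/27 = 3.7 points. If Cohort 1 stopped at 17 and Cohort 2 took the rest, 50 − 17 = 33 and 1/33 = 3.0 points.

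**Step 4: effect on the interval, for an assumed count of 27/27 under the current rule.** The exact Clopper-Pearson lower limit for 27/27 is 0.05^(1/27) = 0.895. The Blyth-Still-Casella column is a numerical approximation.

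| Recoded as failure | Estimate | Lower limit, Clopper-Pearson | Lower limit, BSC (approx.) |
|---|---|---|---|
| 0 | 27/27 = 100% | 0.895 | 0.898 |
| 1 | 26/27 = 96.3% | 0.836 | 0.843 |
| 2 | 25/27 = 92.6% | 0.785 | 0.796 |

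Each recoded participant lowers the limit by about 5 to 6 points. These counts are illustrative; the SAP states no expected SVR or relapse rate.

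**The case against.** The strongest reply is that this is an omission and that the protocol may close it. Whether relapsers may take other HCV therapy while on study, and whether they remain in follow-up, are matters a SAP commonly leaves to the protocol, and only the SAP was examined here. If such participants leave the study, SVR24 largely protects itself, because a missing week 24 sample is a failure with no bracketing. That limits how often the problem could arise. It does not repair the rule: the SAP restates the outcomes and supplies the whole scoring algorithm, and that algorithm gives the wrong answer for anyone who does stay.

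It is also fair to say that a case could not stay hidden. Section 9.1 calls for individual trajectories and an appendix of all HCV RNA values, and section 9.3 lists relapsers. That makes a discordant case visible but leaves the count unchanged.

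Several stronger readings are tempting and are not supported:

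- A reader might infer that the SAP tells the analyst to ignore other therapy. It does not; the effect follows from the absence of an exception.
- A reader might treat any undetectable result after rebound as misclassified. Someone who clears without other therapy meets the time-point definition in section 8.1, and scoring that as failure is a debatable choice of estimand. Reinfection raises the same question.
- The note in section 5 that "undetectable at baseline may indicate spontaneous clearing" might be taken as evidence of clearance after relapse. It concerns the interval between screening and baseline, before treatment.
- The open upper end of the SVR24 window might be taken as the main cause. The sample nearest the target is used, so the open end matters only when no sample exists near day 168.

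**Conclusion.** The concern holds for confirmed relapse followed by non-study HCV therapy. Followed literally, sections 8.1 and 9.2 can count such a participant as an SVR while section 9.3 lists the same person as a relapse. The main exposure is SVR24, which is secondary and descriptive. A reader might infer that the primary SVR12 result, on which the historical comparison in section 2.2 rests, is materially biased. The documents do not support that, because the SVR12 route is narrow and nothing shows that any participant followed it.

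Each case adds 3.7 points at n = 27 (3.0 at n = 33), always in the regimen's favour. The number of cases cannot be determined from the SAP. The conclusion assumes that at least one relapser could start other therapy and still contribute a later sample. The change is worth making because the mechanism is certain and the remedy small.

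**What to change.** Add to sections 8.1 and 9.2 a sentence to this effect: HCV RNA results obtained after the start of non-study HCV therapy do not count towards SVR and may not serve as bracketing measurements; the participant is scored as non-SVR at that and every later time point.

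For confirmed relapse followed by an undetectable result without other therapy, and for suspected reinfection, keep the time-point definition, flag the participant in the SVR tables, and report a sensitivity count that scores the case as failure.

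The cost is one sentence in each section, one programming flag and a footnoted sensitivity count. The flag needs the start date of any non-study HCV therapy. The preliminary dataset list in section 10 names no dataset for it, so the source should be identified. The reported SVR may come out slightly less favourable; there is no other downside.
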